#### **10.4.9.2. Cardiovascular Adverse Events**

CV adverse events are defined as events included in the Embolic and thrombotic events broad SMQ, Ischemic heart disease broad SMQ, or Central nervous system vascular disorders narrow SMQ.

Analyses to be performed specifically for CV events include:

- Incidence of CV TEAEs by SOC and PT
- Incidence of CV TEAEs by PT and presence of CV medical history (yes, no)
- Incidence of CV SAEs by PT and presence of CV medical history (yes, no)
- Incidence of CV SAEs by PT and baseline LDL quartiles
- Incidence of CV SAEs by PT and LDL increase >15% from baseline
- Incidence of CV SAEs by PT and baseline HDL quartiles

#### 10.4.9.4. Serum Chemistry Lipids

Summary statistics will be presented for total cholesterol, LDL, HDL, very low density lipoprotein (VLDL), and triglycerides by visit, as well as worst and last postbaseline value. Plots will also be created for these parameters showing mean values over time. Summary tables will be repeated for the following subgroups:

- Baseline LDL quartiles (Reference categories: <100 mg/dL; 101-103 mg/dL; 131-159 mg/dL; >160 mg/dL)
- Baseline HDL quartiles

Additionally, shift tables from baseline to each post-baseline visit will be presented for HDL and LDL, using the normal and abnormal cutoffs below:

- LDL: normal (<100 mg/dL) and abnormal ( $\geq$ 100 mg/dL)
- HDL: normal ( $\geq$ 40 mg/dL in men, or  $\geq$ 50 mg/dL in women) and abnormal (<40 mg/dL in men or <50 mg/dL in women)

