15.2.6. Laboratory Assessments

Except for Screening and safety lab visits between regularly scheduled visits, subjects will be instructed to attend each study visit in a fasted state, preferably in the morning, and subjects should remain fasted until their blood samples have been collected. For visits that require fasting, the Investigator or designee will verify that the subject has fasted for at least 8 hours and record fasting status in the source and CRF. If the subject reports having eaten (water is permitted) within 8 hours, the Investigator or designee will document accordingly in the source

and CRF and remind the subject that fasting is required before all regularly scheduled study visits after screening (exception – safety lab visits).

Blood, urine, and stool samples for laboratory assessments will be collected at the visits specified in Table 1. Full instructions concerning the number and type of samples to be collected at each visit, the required sample volumes, sample collection methods, sample processing, labeling, and shipping will be provided in separate procedural manuals. All necessary collection supplies will be provided by the appropriate laboratory and will be appropriately assembled for the specific evaluations required at each visit.

If a subject cannot return to the clinic for a scheduled or unscheduled visit, or there is an event that triggers a need for an immediate assessment, the use of a local laboratory is required. In these cases, the Investigator will obtain the laboratory results and the laboratory normal ranges. All local laboratory data, including the reference ranges, are to be collected and entered in the eCRF within 2 days of receiving the results. For guidance on alternative processes under which subjects may complete the protocol-specified assessments under COVID-19 restrictions refer to Section 10.

All subjects with laboratory tests containing clinically significant abnormal values are to be followed regularly until the values return to normal ranges; until a valid reason, other than investigational product-related AE, is identified; or until further follow-up is deemed medically unnecessary.

The list of laboratory analytes to be tested is shown in Table 12.

Table 12: List of Laboratory Analytes to be Tested

Laboratory Assessment	Analyte
All Subjects	

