- Any other factors that are relevant to dyslipidemia management

Recommended LDL Management Algorithm ([Figure A1](#)):

[figure not shown]
- Investigators and/or study staff will be alerted by the central laboratory when a $\geq 15\%$ increase from baseline is detected in a subject's LDL concentration as part of the standard lab panel conducted at every study visit.
 - If an LDL value is elevated and the subject reports having eaten within 8 hours before the blood draw, the Investigator may repeat the assessment under fasting conditions to better assess the magnitude of the increase.

- If the LDL cholesterol increase of $\geq 15\%$ relative to study baseline is confirmed, Investigators should also assess any other cardiovascular disease risk factors that may be present. A subject may be considered at high risk for cardiovascular disease if any of the following factors are present:
 - History of atherosclerotic cardiovascular disease (eg, prior myocardial infarction, angina) or cerebrovascular disease
 - High LDL and/or low high-density lipoprotein values
 - Age >50
 - Diabetes mellitus
 - Hypertension
 - Tobacco smoker
 - Male gender
- If the Investigator determines that intervention is warranted after a risk-benefit analysis for statin versus non-statin dyslipidemia therapy, the Investigator may:
 - Initiate statins at an appropriate dose (high-, moderate-, or low-intensity statin depending on the subject's cardiovascular risk profile) in subjects who are not currently taking a statin
 - Up-titrate statin dose in subjects who are already taking a statin at less than maximum (or maximum tolerated) dose or switch to a more potent statin in subjects taking maximum dose of a low or moderate intensity statin
 - Initiate or up-titrate non-statin dyslipidemia therapy in subjects for whom statin use is not preferred or are already on a maximum (or maximum tolerated) statin therapy (eg, ezetimibe, fibrates, PCSK9 inhibitors, and bile acid sequestrants [see protocol for instructions regarding dosing of investigational product and bile acid sequestrants])
- If any dyslipidemia therapy is initiated or up-titrated:
 - The new concomitant medication or change in dose must be documented on the case report form (CRF);
 - Dyslipidemia therapy initiation or dose adjustments may be considered appropriate to achieve LDL concentrations at or below baseline

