#### **4.2. Baseline Definitions**

The baseline value for statistical analyses of quantitative parameters (except lipoprotein evaluations and markers of glucose metabolism) is defined as the mean of all available evaluations, at the individual subject level, prior to the first administration of investigational product, unless otherwise specified. If there is only one evaluation prior to the first administration of investigational product, then the available data from this evaluation will be used as the baseline value. Quantitative parameters include, but are not limited to, lab parameters (except lipoprotein evaluations and markers of glucose metabolism), electrocardiogram measures, exploratory biomarkers, pharmacodynamic parameters, and vital signs.

The baseline value for analyses of lipid parameters and markers of glucose metabolism is defined as the last fasted evaluation prior to the first administration of investigational product, unless otherwise specified.

The baseline value for analyses of qualitative parameters (eg, normal/abnormal), cardiovascular risk assessments, and patient-reported outcomes is defined as the last evaluation prior to the first administration of investigational product. Baseline definition of each assessment is provided in [Appendix A](#).

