#### 10.4.5. Pancreatitis

Treatment-emergent adverse events of pancreatitis, defined by Acute Pancreatitis narrow SMQ, will be summarized as follows:

- Incidence of pancreatitis TEAEs, by PT and presence of Gallbladder disease and Related Complications medical history (yes, no)
- Incidence of pancreatitis TEAEs, by PT and presence of Pancreatitis (acute or chronic) medical history (yes, no)
- Incidence of pancreatitis TEAEs by PT and presence of Gallbladder disease and Related Complications TEAE (occurring before or simultaneous to Pancreatitis TEAE)
- Incidence of pancreatitis TEAEs by glucagon-like peptide-1 (GLP-1) agonist use (never used, baseline use, initiated during study, baseline use or initiated during study); Note: GLP-1 use initiated during study will only be counted if initiated prior to onset of first pancreatitis TEAE.
- Incidence of pancreatitis TEAEs by shift from baseline to worst post-baseline triglycerides >1000 mg/dL. Note: Only the worst post-baseline triglycerides measurement recorded prior to onset of first pancreatitis TEAE is utilized.
- KM plot for time to onset of first pancreatitis TEAE
- KM plot of pancreatitis cases with on treatment gallbladder Disease or related complications (occurring before or simultaneous to Pancreatitis)

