### **10.5.1. Serum Chemistry, Hematology, and Coagulation**

Quantitative serum chemistry (including calculated eGFR), hematology, and coagulation results by treatment group using descriptive statistics at baseline and at each on-study evaluation. The laboratory values, change, and percentage change from baseline, will also be summarized. Baseline is defined as the mean of all available evaluations prior to treatment.

Shifts in CTCAE toxicity grade of laboratory tests from baseline to worst value (scheduled or unscheduled), last value (scheduled or unscheduled), and at each scheduled post-baseline visit will be provided. The toxicity grades are in the CTCAE version 4.03.

Summaries will present the number and percentage of subjects with shifts in laboratory toxicity grade by treatment group.

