#### **10.5.5. Lipoprotein Evaluations**

Serum chemistry-based assessments are the standard safety tool for monitoring subjects’ serum lipids. Additional lipoprotein samples, separate from the serum chemistry samples, will be obtained and assayed in addition to the serum chemistry panel lipid assay.

The lipoprotein analyte values, change from baseline, and percentage change from baseline will be summarized by treatment group for the lipoprotein analytes. Baseline is defined as the last fasting assessment before treatment. This analysis will use only samples that have a confirmed fasting of approximately 8 hours or more before their visit.

Analyses of quantitative lipoprotein analytes will be carried out using MMRM as described in the General Statistical Methods ([Section 4](#)).

Subgroup analysis by statin use (no concomitant statin use, statin use started prior to first dose of investigational product and statin use started after first dose of investigational product) will be performed. In addition to statin use, similar subgroup analyses will be performed by use of other antihyperlipidemic drugs. Only descriptive statistics will be provided.

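### SAP 10.4.9.4 prints baseline LDL bands with gaps and calls them quartiles, the SAP gives two baseline rules for serum-chemistry lipids, and post-baseline lipid values carry no fasting rule

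*SAP*

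**What the plan says.** **Values summarised.** SAP 10.4.9.4 covers total cholesterol, LDL, HDL, VLDL and "triglycerides by visit, as well as worst and last postbaseline value".

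**LDL subgroups.** SAP 10.4.9.4 repeats the serum lipid tables by "Baseline LDL quartiles (Reference categories: <100 mg/dL; 101-103 mg/dL; 131-159 mg/dL; >160 mg/dL" and by baseline HDL quartiles. SAP 10.4.9.2 tabulates cardiovascular SAEs by baseline LDL quartiles and does not define them.

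**Baseline.** SAP 4.2: "The baseline value for analyses of lipid parameters and markers of glucose metabolism is defined as the last fasted evaluation" before first dose. SAP 10.5.1, for serum chemistry: "Baseline is defined as the mean of all available evaluations prior to treatment". The baseline table in SAP Appendix A follows the mean rule for serum chemistry and gives the last fasted assessment only for a row headed Lipoprotein. Protocol Table 12 lists LDL, HDL, VLDL, total cholesterol and triglycerides under serum chemistry.

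**Fasting after baseline.** SAP 10.5.5, on the separate lipoprotein samples: "This analysis will use only samples that have a confirmed fasting of approximately 8 hours or more before their visit". No such condition appears in SAP 10.4.3 (LDL rise of at least 15%), 10.4.5 (triglycerides above 1000 mg/dL before pancreatitis) or 10.4.9.4. On collection, Protocol 15.2.6 says: "Except for Screening and safety lab visits between regularly scheduled visits, subjects will be instructed to attend each study visit in a fasted state". Fasting status goes on the CRF.

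**The concern.** LDL rise is a recognised effect of this drug. Protocol 5.3 reports an increase of about 20% to 25% by Week 4 across the OCA groups of Study 747-209, and Protocol 5.5 says the clinical meaning of the lipid changes is not well understood. The serum-chemistry panel is the lipid source that covers the whole trial. Protocol 16.9.6 limits the separate lipoprotein samples, which do carry a fasting filter, to a subset collected up to protocol Version 7.

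Three things are at stake:

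- A programmer who follows the printed bands drops subjects with mid-range LDL from the subgroup tables.
- Two programmers who each follow a valid part of the SAP can derive different baselines. They would then disagree on every change, shift and LDL ≥15% result.
- A post-baseline value drawn after food can be set against a fasted baseline, and a worst-value statistic can rest on that one draw.

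**Working it through.** The plan states no figure on this point, so there is none to reproduce.

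**1. Which LDL values have no band.** Check each whole number from 90 to 199 mg/dL against the four printed bands. Unassigned: 100 (1 value), 104 to 130 (27 values) and 160 (1 value), so 1 + 27 + 1 = 29. If the second band is read as 101-130, only 100 and 160 remain.

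**2. How many subjects that could be.** The documents give no baseline LDL mean or SD; those below are assumptions. With LDL reported in whole mg/dL and a normal distribution with mean m and SD s:

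share in 104-130 = Φ((130.5 − m)/s) − Φ((103.5 − m)/s)

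For m = 110, s = 35: Φ(20.5/35) − Φ(−6.5/35) = Φ(0.586) − Φ(−0.186) = 0.721 − 0.426 = 0.295.

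| Assumed mean / SD (mg/dL) | In 104-130 | In 101-103 | No band, as printed | No band if 101-130 was meant |
|---|---|---|---|---|
| 100 / 40 | 24.2% | 3.0% | 25.5% | 1.3% |
| 110 / 35 | 29.5% | 3.3% | 31.0% | 1.5% |
| 115 / 35 | 30.0% | 3.2% | 31.5% | 1.5% |
| 120 / 40 | 26.4% | 2.7% | 27.8% | 1.5% |

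The fourth column adds those at exactly 100 or 160 to the second. Over every whole-number mean from 95 to 130 and SD from 30 to 45, with normal and lognormal shapes, the share in 104-130 runs from 16.3% to 37.0%. It exceeds 25% in 70% of the normal cases and 61% of the lognormal ones. With a normal shape and SD 45 it never exceeds 23.6%. Contiguous bands or true sample quartiles leave 0% unassigned.

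**3. Which baseline applies.**

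- SAP 4.2 names lipid parameters for the fasted rule. Its own exception to the mean rule, however, names lipoprotein evaluations, and SAP 10.5.5 treats those as separate samples.
- SAP 10.5.1, SAP Appendix A and Protocol 16.9.5 apply the mean rule to serum chemistry or laboratory parameters generally. Table 12 places the lipids there.
- Protocol 9.9.3 draws serum chemistry at Screening, which Protocol 15.2.6 exempts from fasting. The mean rule can therefore include a fed value.

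**4. Where unfasted post-baseline values can enter.**

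- Scheduled visits: an 8-hour fast is required after Screening. A subject who has eaten is recorded as such and reminded; nothing says to discard the sample.
- Fed LDL draws are foreseen. Protocol Appendix A says that "the Investigator may repeat the assessment under fasting conditions to better assess the magnitude of the increase". SAP 4.3 then picks the assessment nearest the target date whatever its fasting status, so the fed value can be the one kept.
- Unscheduled visits may include serum biochemistry at the investigator's discretion (Protocol 9.9.10). The COVID-19 minimum testing includes a lipid panel, possibly at a local laboratory, with no fasting condition stated (Protocol 10.1). SAP 10.5 puts local results in the datasets.
- SAP 10.5.1 counts unscheduled values as worst or last for toxicity-grade shifts. SAP 10.4.9.4 does not say either way.
- In SAP 10.4.5, "Only the worst post-baseline triglycerides measurement recorded prior to onset of first pancreatitis TEAE is utilized": one value per subject, so a single fed draw can decide the category.

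The documents give neither the share of fed samples nor the size of a fed effect, so no magnitude can be computed for steps 3 and 4.

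**The case against.** The other side has a good deal right.

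- *Most post-baseline data are fasted by design.* Fasting is required and checked at scheduled visits. This stands, and it confines the problem to non-compliant and unscheduled draws and to worst and last values.
- *The trigger panels carry no lipids.* A reader might infer that an arm with more liver or renal triggers would feed more fed lipid values into its worst-value statistics. The repeat panels in Protocol 7.4.1, 7.4.3 and 7.6.1 name liver, coagulation, electrolyte and renal tests, not lipids. The documents do not support a bias that differs by arm.
- *A specific rule beats a general one.* On that reading SAP 4.2 governs the lipid baseline. It is the likelier intent, but Appendix A's fasted row says only Lipoprotein, so the text does not settle it.
- *101-103 is a slip.* Placed directly before 131-159, it probably stands for 101-130. Even so, 100 and 160 stay unassigned, and the choice between fixed bands and quartiles stays open.
- *Little depends on these tables.* SAP 10 plans no inferential safety comparison unless specified. The overall lipid tables keep everyone, the LDL shift table (below 100, 100 or above) has no gap, and SAP 10.4.3 also requires a sustained LDL rise over two or more consecutive visits. All true; this limits the importance without repairing the text.
- *A fasted-only rule could discard the extremes.* This holds for triglycerides above 1000 mg/dL, and the remedy allows for it.

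**Conclusion.** The point holds as three defects in the SAP text: LDL bands with gaps under the wrong label, two competing baselines for the same analytes, and no fasting rule for post-baseline serum lipids.

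The size of the first depends on the reading: 16%-37% of subjects in 104-130 as printed, about 1.5% if a slip is corrected, none under true quartiles. The percentages rest on the assumed LDL means, SDs and shapes. A reader might infer that over a quarter of subjects would drop out. That is plausible under many of the assumed distributions, but the documents cannot establish it.

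A reader might also infer that lipid change is distorted. The documents show only that it could be affected, through a limited set of samples, by an amount and in a direction they do not give. The primary endpoint, the alpha allocation and the sample size are untouched. The wording should still be corrected, because following it as written gives incomplete or irreproducible safety tables.

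**What to change.** 1. In SAP 10.4.9.4, use contiguous LDL bands (<100, 100 to <130, 130 to <160, ≥160 mg/dL) or true quartiles. Say which, and use the same definition in 10.4.9.2.
2. State in SAP 10.5.1 and Appendix A that serum-chemistry lipids take the last fasted pre-dose value, as in 4.2.
3. For change from baseline, shift and LDL ≥15% analyses, use post-baseline samples with confirmed fasting, as 10.5.5 does, and give an all-samples supportive table.
4. For triglycerides above 1000 mg/dL in SAP 10.4.5, keep all samples and add a fasted-only sensitivity table.
5. State whether worst and last lipid values include unscheduled and local-laboratory results.

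Cost: SAP wording and a filter on a status already collected on the CRF. Somewhat fewer post-baseline values enter the main lipid tables, and a subject with no fasted pre-dose sample has no lipid baseline.

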### 10.5. Clinical Laboratory Evaluations

Laboratory parameters will be summarized in both conventional units and the standard international (SI) system of units. Analysis of efficacy-related liver biochemistry endpoints is specified in [Section 6.4.6.3](#).

The submitted datasets will also include results from local lab evaluations and these values will be flagged in the ADLB dataset with the flag variable LOCALFL="Y". Dataset with conventional units will be labelled using standardized names (e.g. ADLB) and the one with SI units will be labelled by adding "SI" to the file name (e.g. ADLBSI).

All clinical laboratory data will be presented in by-subject data listings.

### **10.5.1. Serum Chemistry, Hematology, and Coagulation**

Quantitative serum chemistry (including calculated eGFR), hematology, and coagulation results by treatment group using descriptive statistics at baseline and at each on-study evaluation. The laboratory values, change, and percentage change from baseline, will also be summarized. Baseline is defined as the mean of all available evaluations prior to treatment.

Shifts in CTCAE toxicity grade of laboratory tests from baseline to worst value (scheduled or unscheduled), last value (scheduled or unscheduled), and at each scheduled post-baseline visit will be provided. The toxicity grades are in the CTCAE version 4.03.

Summaries will present the number and percentage of subjects with shifts in laboratory toxicity grade by treatment group.

### **10.5.2. Shifts in CTCAE Toxicity Grade**

Shifts in CTCAE toxicity grade of laboratory tests from baseline to worst value (scheduled or unscheduled), last value (scheduled or unscheduled), and at each scheduled post-baseline visit will be provided. The toxicity grades are in the CTCAE Version 4.03.

Summaries will present the number and percentage of subjects with shifts in laboratory toxicity grade by treatment group.

### **10.5.3. Urine Chemistry and Urinalysis**

Quantitative urine chemistry and urinalysis results by treatment group using descriptive statistics at baseline and at each on-study evaluation. The lab results and percentage change from baseline will also be summarized. Baseline is defined as the mean of all available evaluations prior to treatment.

### **10.5.4. Liver Laboratory Criteria for Monitoring for Suspected Hepatic Injury or Decompensation**

The evaluation of hepatic safety will include the following laboratory parameters: ALT, AST, and ALP, GGT, total bilirubin, direct bilirubin, albumin, INR of prothrombin time, and platelets.

Summary statistics will be presented by visit, including change from baseline and percent change from baseline. In addition, mean values of ALT, AST, ALP, GGT, total bilirubin, direct bilirubin, and albumin will be plotted over time.

Summaries will be repeated by baseline fibrosis stage.

In addition, the hepatic safety parameters noted above will be utilized to present analyses of worst post-baseline elevations. EAIR will be presented for each of the following parameters/criteria at any post-baseline visit:

- ALT ( $\geq$ ULN,  $\geq$ 3x ULN,  $\geq$ 5x ULN,  $\geq$ 10x ULN,  $\geq$ 20x ULN, or an increase of 250 U/L from baseline)
- AST ( $\geq$ ULN,  $\geq$ 3x ULN,  $\geq$ 5x ULN,  $\geq$ 10x ULN,  $\geq$ 20x ULN, or an increase of 250 U/L from baseline)
- ALP ( $\geq$ 2x ULN,  $\geq$ 3x ULN, or an increase of 150 U/L from baseline)

- Total Bilirubin ( $\geq 2x$  ULN,  $\geq 5x$  ULN,  $\geq 8x$  ULN, or an increase of 2 mg/dL from baseline)
- Direct Bilirubin ( $\geq 2x$  ULN,  $\geq 5x$  ULN, or an increase of 1 mg/dL from baseline)
- GGT ( $\geq 2x$  ULN)
- INR ( $\geq 1.5x$  ULN,  $\geq 3x$  ULN,  $\geq 5x$  ULN)

Evaluation of drug-induced serious hepatotoxicity (eDISH) will be conducted to visually compare maximum ALT and total bilirubin values at any post-baseline visit. For subjects with baseline ALT or total bilirubin levels above ULN, eDISH plots will also be generated based on multiples of elevations above the baseline (BL) value ( $2 \times BL$  and  $3 \times BL$  for ALT, and  $2 \times BL$  for total bilirubin).

Similar eDISH analysis as described above will be performed for ALP and total bilirubin. Plots based on multiples of elevations above the baseline value will use  $2 \times BL$  for ALP and  $2 \times BL$  for total bilirubin.

The summary table as well as visual plots will be based on central lab data. eDISH using maximum post-baseline ALT and total bilirubin will be repeated with central and local lab data.

In addition, EAIR will be presented for each of the following biochemical triggers for potential DILI by treatment group using the worst post-baseline elevations. For subjects with normal baseline liver biochemistry:

- (ALT  $\geq 3x$  ULN or AST  $\geq 3x$  ULN) and total bilirubin  $\geq 2x$  ULN
- ALT  $\geq 5x$  ULN or AST  $\geq 5x$  ULN
- ALT  $\geq 8x$  ULN or AST  $\geq 8x$  ULN
- (ALT  $\geq 3x$  ULN or AST  $\geq 3x$  ULN) and INR  $> 1.5$
- ALP  $\geq 2x$  ULN and direct bilirubin  $\geq 2x$  ULN
- GGT  $\geq 2x$  ULN and direct bilirubin  $\geq 2x$  ULN

For subjects with elevated BL liver biochemistry:

- (ALT  $\geq 3x$  BL or AST  $\geq 3x$  BL) and total bilirubin  $\geq 2x$  BL
- ALT  $\geq 3x$  BL or AST  $\geq 3x$  BL
- ALT  $\geq 5x$  BL or AST  $\geq 5x$  BL
- (ALT  $\geq 2x$  BL or AST  $\geq 2x$  BL) and INR  $> 1.5$
- ALP  $\geq 2x$  BL and ALP  $> ULN$  and direct bilirubin  $\geq 2x$  BL and direct bilirubin  $> ULN$
- GGT  $\geq 2x$  BL and GGT  $> ULN$  and direct bilirubin  $\geq 2x$  BL and direct bilirubin  $> ULN$

For the above summaries the following triggers will be also considered to allow identification of subjects in whom abnormalities were not detected using elevations relative to baseline:

- Trigger 1: BL ALT + 250 U/L
- Trigger 2: BL AST +250 U/• Trigger 3: BL ALT + 150 U/L and BL total bilirubin + 2 mg/dL
- Trigger 4: BL AST + 150 U/L and BL direct bilirubin + 1 mg/dL
- Trigger 5: BL AST or ALT + 150 U/L and BL total bilirubin + 2 mg/dL
- Trigger 6: BL AST or ALT + 150 U/L and INR >1.5
- Trigger 7: BL AST or ALT + 100 U/L and BL total bilirubin + 2 mg/dL and INR >1.5
- Trigger 8: BL ALP + 150 U/L and BL TB + 2 mg/dL
- Trigger 9: BL ALP + U/L and Baseline direct bilirubin + 1 mg/dL
- Trigger 10: BL total bilirubin + 2 mg/dL
- Trigger 11: BL direct bilirubin + 1 mg/dL
- Trigger 12: INR >1.5 (confirmed with repeat test and not responsive to vitamin K administration)

Any elevation  $\geq 1.5$ x ULN will be categorized as a “elevated” baseline value. For these analyses, the following ULN thresholds will be used:

- ALT – 30 U/L
- AST – 35 U/L
- Total Bilirubin – 1.25 mg/dL
- Direct bilirubin – 0.3 mg/dL
- ALP – 120 IU/L

A summary of the number (%) of subjects who met the stopping criteria provided in Table 3 of the protocol (see [Appendix D](#)) will be presented by treatment group and each of the criteria. A listing of these subjects with the associated laboratory parameters will be presented along with the action taken with the study drug and flags to denote values or subjects that meet the proposed mitigation criteria for DILI.

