	ALT $\geq 2x$ BL or ≥ 300 U/L, whichever occurs first Regardless of TB or DB	Yes	Interrupt 
 Repeat laboratory testing including CPK within 2-4 days Collect PK sample within 7 days
	ALT $\geq 5x$ BL or ≥ 500 U/L, whichever occurs first Regardless of TB or DB	No	Interrupt 
 Repeat laboratory testing including CPK within 2-4 days Collect PK sample within 7 days
	ALT $\geq 2x$ BL or ≥ 300 U/L, whichever occurs first TB $\geq 2x$ ULN Gilbert's ^c : DB $>2x$ ULN or INR >1.5	No	Interrupt 
 Repeat laboratory testing including CPK within 2-4 days Collect PK sample within 7 days
TB (>1.5 mg/dL exclusion criterion 747-303)	TB ≥ 2.0 mg/dL and DB $>30\%$ of TB	Yes/No	Interrupt 
 Repeat laboratory testing including CPK within 2-4 days Collect PK sample within 7 days

Table 2: Liver Laboratory Criteria for Monitoring for Potential Hepatic Injury (Continued)

Baseline	Treatment Emergent	Signs and Symptoms of Hepatic Injury ^a	Action
ALP ≤ULN ^d	ALP ≥2x BL and >ULN	No	
If ALP <250 U/L, then:
 
 Repeat laboratory testing including CPK within 2-4 days 
If ALP ≥250 U/L, then:
 
Interrupt
 
 Repeat laboratory testing including CPK within 2-4 days Collect PK sample within 7 days
		Yes	
Interrupt
 
 Repeat laboratory testing including CPK within 2-4 days Collect PK sample within 7 days
ALP >ULN ^d	ALP ≥2x BL or >300 U/L, whichever occurs first	No	
If ALP <300 U/L, then:
 
 Repeat laboratory testing including CPK within 2-4 days 
If ALP ≥300 U/L, then:
 
Interrupt
 
 Repeat laboratory testing including CPK within 2-4 days Collect PK sample within 7 days
		Yes	
Interrupt
 
 Repeat laboratory testing including CPK within 2-4 days Collect PK sample within 7 days

ALP = alkaline phosphatase; ALT = alanine aminotransferase; BL = baseline; DB = direct bilirubin; CPK = creatine phosphokinase; DILI = drug-induced liver injury; INR = international normalized ratio; NASH = nonalcoholic steatohepatitis; OCA = obeticholic acid; PK = pharmacokinetic; TB = total bilirubin; ULN = upper limit of normal

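### SAP 10.5.4: the combined enzyme-and-bilirubin trigger for elevated-baseline subjects has no above-ULN condition on total bilirubin, so some values within the normal range can meet its bilirubin limb

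*SAP*

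**What the plan says.** SAP 10.5.4 lists laboratory triggers for potential drug-induced liver injury (DILI) and reports an EAIR for each by treatment group, using worst post-baseline values. There is one list for normal baselines and one introduced by "For subjects with elevated BL liver biochemistry".

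Three rows of the second list involve bilirubin:

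- Combined transaminase row: "ALT $\geq 3x$ BL or AST $\geq 3x$ BL) and total bilirubin $\geq 2x$ BL".
- ALP row: "ALP $\geq 2x$ BL and ALP $> ULN$ and direct bilirubin $\geq 2x$ BL and direct bilirubin $> ULN".
- GGT row: "GGT $\geq 2x$ BL and GGT $> ULN$ and direct bilirubin $\geq 2x$ BL and direct bilirubin $> ULN".

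The matching combined row for normal baselines is "ALT $\geq 3x$ ULN or AST $\geq 3x$ ULN) and total bilirubin $\geq 2x$ ULN". The same section fixes the ULN for these analyses at "Total Bilirubin – 1.25 mg/dL". It defines an elevated baseline in a sentence that begins "Any elevation $\geq 1.5$ x ULN will be categorized as a", without saying whether this applies analyte by analyte or to a subject with any elevated analyte.

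For subjects with elevated baseline ALT, the monitoring table (Protocol Table 2, reproduced in SAP Appendix D) makes the enzyme relative to baseline but keeps bilirubin relative to ULN: "ALT $\geq 2x$ BL or ≥ 300 U/L, whichever occurs first TB $\geq 2x$ ULN".

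**The concern.** The elevated-baseline list exists because a multiple of ULN works badly for a subject whose ALT or AST is already high. A subject can have high ALT and normal bilirubin, however, and for that subject doubling a low baseline bilirubin may leave the value inside the normal range. The ALP and GGT rows guard against this by also requiring direct bilirubin above ULN. The total-bilirubin row has no such guard.

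What is at stake is the meaning of one by-arm rate. A reader will take a transaminase-plus-bilirubin category to describe enzyme elevation with abnormal bilirubin. As written, it can include subjects whose bilirubin never left the normal range, and it means something different from the matching category for normal baselines. Protocol 5.5 reports that serious hepatic events were more frequent with OCA 25 mg, so by-arm hepatic tables are likely to be read closely.

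**Working it through.** The plan gives no figure to reproduce; the check is threshold arithmetic from its own cut-offs.

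**Inputs**

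| Input | Value | Source |
|---|---|---|
| ULN, total bilirubin | 1.25 mg/dL | SAP 10.5.4 |
| ULN, ALT | 30 U/L | SAP 10.5.4 |
| Elevated baseline | ≥1.5 × ULN | SAP 10.5.4 |
| Bilirubin limb, elevated baseline | ≥2 × baseline | SAP 10.5.4 |
| Bilirubin limb, normal baseline | ≥2 × ULN = 2.5 mg/dL | SAP 10.5.4 |
| Eligibility cap, total bilirubin | >1.5 mg/dL excluded, except Gilbert's syndrome | Protocol 8.1.2, criterion 6 |

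**1. Which reading of an elevated baseline is workable?** If it applied to each analyte separately, the bilirubin limb would need a baseline of at least 1.5 × 1.25 = 1.875 mg/dL. The eligibility cap is 1.5 mg/dL, or 1.5/1.25 = 1.2 × ULN, so outside Gilbert's syndrome that group would be almost empty. Two other features point to the any-analyte reading. The ALP row's above-ULN condition would be redundant if ALP itself had to be elevated at baseline. The baseline-relative eDISH plots in the same section also form their group from ALT or total bilirubin, although with a cut at ULN and not at 1.5 × ULN.

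**2. When can a normal value meet the limb?** When 2 × baseline ≤ ULN, so baseline ≤ 1.25/2 = 0.625 mg/dL. The baselines below are illustrative; the documents give no distribution.

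| Baseline (mg/dL) | Limb met from (mg/dL) | × ULN | With above-ULN condition |
|---|---|---|---|
| 0.3 | 0.6 | 0.48 | >1.25 |
| 0.4 | 0.8 | 0.64 | >1.25 |
| 0.5 | 1.0 | 0.80 | >1.25 |
| 0.6 | 1.2 | 0.96 | >1.25 |
| 0.8 | 1.6 | 1.28 | 1.6 (unchanged) |
| 1.0 | 2.0 | 1.60 | 2.0 (unchanged) |
| 1.25 | 2.5 | 2.00 | 2.5 (unchanged) |

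Above a baseline of 0.625 mg/dL the added condition changes nothing. For any baseline below 1.25 mg/dL the limb as written is looser than the 2.5 mg/dL used for normal baselines.

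**3. What does a baseline multiple miss?** A baseline of 1.4 mg/dL is eligible. A rise to 2.6 mg/dL is 2.6/1.25 = 2.08 × ULN but 2.6/1.4 = 1.86 × baseline, so it fails the row with or without the above-ULN condition. The combined Triggers 3 and 5 do not recover it, because they need baseline plus 2 mg/dL, here 3.4 mg/dL.

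**4. How far does the effect spread?** The next row in the list is ALT or AST ≥3 × baseline with no bilirubin condition. Everyone who meets the combined row already meets that one, so the missing condition adds nobody to the overall potential-DILI set. It changes only who falls in the combined category.

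**The case against.** The strongest reply is that this is one row in a descriptive screening table, well covered elsewhere. Much of that stands.

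- The hepatic safety objective is adjudicated hepatic injury. SAP 10.4.2 sends identified cases to the Hepatic Safety Adjudication Committee and plans separate analyses of its results. SAP Section 10 rules out inferential safety comparisons unless specified. This row does not carry the hepatic assessment.
- The enzyme limb is demanding. With baseline ALT at or above 1.5 × 30 = 45 U/L, the ALT limb needs at least 135 U/L, or 4.5 × ULN. Nobody qualifies on bilirubin alone.
- The Appendix D criteria are already to be summarised as number and percentage by arm, total bilirubin ≥2 × ULN has its own EAIR, and maximum ALT is plotted against maximum bilirubin. However, none of the listed EAIR rows combines an enzyme rise with total bilirubin ≥2 × ULN in the elevated-baseline group.
- The baseline-relative eDISH plots also use 2 × baseline for total bilirubin with no above-ULN condition, so the row may be deliberate. That weakens the case for a drafting slip. It does not explain why the ALP and GGT rows differ.

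Triggers 1 to 12 and adjudication do not cure the problem. The former are considered in addition, and the latter is a separate step that does not filter this EAIR.

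**Conclusion.** The point holds in a limited form. On the any-analyte reading, the row lets a subject with baseline total bilirubin of 0.625 mg/dL or less meet the bilirubin limb at or below ULN. This can inflate the by-arm EAIR of the combined enzyme-plus-bilirubin category and nothing else. The conclusion rests on that reading, which the SAP favours but does not state. The number of affected subjects is unknown: the documents give neither the baseline bilirubin distribution nor the frequency of threefold enzyme rises.

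A reader might infer more, without support from the documents:

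- That normal bilirubin is being counted as serious liver injury. The SAP's label is potential DILI, and the enzyme limb must also be met.
- That this is the main hepatic safety count. Adjudicated injury is the stated objective.
- That a true difference between arms would be diluted. No rates are given from which to judge this.
- That the row ought to agree with Appendix D. The two also differ in ALT multiple, in the 300 U/L alternative and in possible re-baselining from Months 3 and 6, so disagreement alone is not an error.

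The dosing rules and the primary endpoint are unaffected. A wording change is worth making before the tables are produced.

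**What to change.** Make three changes in SAP 10.5.4:

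1. Amend the bilirubin limb of the combined elevated-baseline row to total bilirubin ≥2 × baseline and also above ULN, in line with the ALP and GGT rows.
2. State that an elevated baseline means any analyte at or above 1.5 × ULN.
3. Add an EAIR row for this group with ALT or AST ≥3 × baseline and total bilirubin ≥2 × ULN. The above-ULN condition removes normal values but does not recover cases such as 1.4 to 2.6 mg/dL; this row does when the enzyme limb is met.

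No new data are needed. The combined count can only stay the same or become smaller. SAP Section 11 says additional hepatic laboratory analyses were produced for the Month 18 resubmission and will be repeated at end of study. If this row was among them, the amended row will not be comparable with that table, and it will also differ from the 2 × baseline eDISH plots. Showing the present row beside the amended one keeps both comparisons.
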